1.9.3 Examiner calibration

For inter-examiner validity, 20 randomised lateral cephalometric images were traced by the principal investigator ([name]) and compared with tracings by an experienced orthodontist, serving as the reference standard. For intra-examiner reliability, the principal investigator repeated tracings of the same 20 images two weeks after the initial session. Linear and angular measurement differences were recorded and tabulated. Intra-class correlation coefficients (ICC) were interpreted according to Koo & Li (2016) as shown in Table 3.8.

Table 3.8 Interpretation of intra-class correlation coefficient (ICC)

ICC Score	Interpretation
<0.5	Poor agreement
0.5 to < 0.75	Moderate agreement

0.75 to <0.9

Good agreement

0.9 to 1.0

Excellent agreement

1.10 Data analysis

All data were recorded using a standardised data collection form. The information was subsequently entered into Microsoft Excel to generate a master dataset, which was then coded and exported into SPSS software version 26.0 (IBM Corp., Armonk, NY, USA) for statistical analysis. Descriptive statistics were computed to summarise study variables such as age and gender.

1.10.1 Statistical Tests

For all statistical tests, the level of significance was set at $p\text{-value} < 0.05$ with a 95% confidence interval. In addition, results with $p\text{-value} < 0.001$ were considered highly significant to further emphasise the strength of these findings.

For within-group comparisons of skeletal, dentoalveolar, and soft tissue changes between the pre-treatment phase (T0) and immediately after the advancement phase (T1), paired t-tests were performed for all the normally distributed data, and for between-group comparisons of skeletal, dentoalveolar, and soft tissue changes, one-way ANOVA was employed.

For assessment of participants' perceptions, responses to the questionnaire were recorded as follows: "never" = 1, "hardly ever" = 2, "sometimes" = 3, "fairly often" = 4, and "very often" = 5. Total scores were computed and compared between pre- and post-intervention using paired t-tests. One-way ANOVA was employed for comparisons between intervention and control groups.

For intra-rater and inter-rater reliability, the Intra-class Correlation Coefficients (ICC) score was employed to assess the reliability and accuracy of the measurement. The ICC score was interpreted according to Koo & Li (2016).

Table 3.11 Statistical analysis of this study

Objectives	Variables	Statistics
Objective 1	Changes in the skeletal effects at pre- and post-intervention: SNA (°), SNB (°), ANB (°), Wit's analysis (mm), Co-Gn (mm), SN-Maxillary Plane (°), SN-Mandibular Plane (°), Maxillary-Mandibular Plane (°)	Paired t-test
Objective 1	Changes in the skeletal effects of the three groups: SNA (°), SNB (°), ANB (°), Wit's analysis (mm), Co-Gn (mm), SN-	ANOVA test

	Maxillary Plane (°), SN-Mandibular Plane (°), Maxillary-Mandibular Plane (°)	
Objective 2	Changes in the dentoalveolar effects at pre- and post-intervention: Overjet (mm), Overbite (%), Upper incisor angle (°), Lower incisor angle (°), Inter-incisor angle (°)	Paired t-test
Objective 2	Changes in the dentoalveolar effects of the three groups: Overjet (mm), Overbite (%), Upper incisor angle (°), Lower incisor angle (°), Inter-incisor angle (°)	ANOVA test
Objective 3	Changes in the soft tissue effects at pre- and post-intervention: Upper lip-E-line (mm), Lower lip-E-line (mm), Nasolabial angle (°).	Paired t-test
Objective 3	Changes in the soft tissue effects of the three groups: Upper lip-E-line (mm), Lower lip-E-line (mm), Nasolabial angle (°).	ANOVA test
Objective 4	Participant's perception (pre- and post-intervention)	Paired t-test
Objective 4	Participant's perception (intervention groups vs control group)	ANOVA test

Intra-rater reliability	Intra-class-correlation (ICC)
Inter-rater reliability	Intra-class-correlation (ICC)

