1.2.2 Sample size calculations

The sample size was calculated based on the standard deviation of the Wit's analysis value from a previous study by Hassan Al Subaie et al. 2023. The value was chosen for sample size calculation because it is one of the parameters that was included in this study and is significant in assessing the skeletal pattern of the participant. The sample size is calculated using G*Power software 3.1.9.7, with the consideration of α equals to 0.05, with the power set to 80%, and an effect size of 1.83mm is used. Thus, the sample size per group is 5, and the total sample size needed is 15 participants (2 intervention groups and 1 control group). This number is increased by 30% to account for the attrition range to produce the final sample size of 21 (7 samples in each group).

[figure not shown]

Figure 3.2 Sample size calculation

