1.3 Inclusion and exclusion criteria

Participants were selected from May 2024 to May 2025 at the Orthodontic Postgraduate Clinic, Universiti Malaya, and screened according to the inclusion and exclusion criteria outlined in Table 3.1 and Table 3.2:

Table 3.1 Inclusion criteria of the participants

Inclusion Criteria	
1	Cervical Vertebrae Maturity: CS3-CS4 (Growing participants)
2	Chronological age: 10-14 years old (Female), 12-16 years old (Male)
3	Average or reduced lower anterior facial height (LAFH<57%)
4	Mild to moderate skeletal Class II ($4^{\circ}<ANB<9^{\circ}$)
5	Retrognathic mandible ($SNB<78^{\circ}$)
6	Increased overjet ($7\text{mm}\leq OJ\leq 11\text{mm}$)
7	Increased overbite by more than 30%
8	Molar relationship by more than $\frac{1}{2}$ unit Class II bilaterally
9	Mild to moderate crowding

Table 3.2 Exclusion criteria of the participants

Exclusion criteria	
1	Participant with an anterior open bite
2	Participant with syndromic dentofacial anomalies
3	Participant with a previous history of orthodontic intervention
4	Participant with signs and symptoms of temporomandibular disorder

- 5 Participant with severe facial asymmetry (Deviation $\geq 4\text{mm}$)
 - 6 Not being consented to by both parents and participants
 - 7 Poor quality of pre-treatment Lateral Cephalometric records
 - 8 Participant with mental or physical disabilities affecting the ability to wear an appliance
-

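### Table 3.11 sets 17 unranked between-arm ANOVAs at 0.05 with no primary outcome or adjustment; separately, its paired tests cannot separate the appliance from growth

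*Combined protocol and SAP*

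**What the plan says.** Section 1.10.1 sets a single level for everything: "For all statistical tests, the level of significance was set at" p < 0.05. Results below 0.001 "were considered highly significant to further emphasise the strength of these findings"; that is a label, not an adjustment.

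Table 3.11 lists 8 skeletal, 5 dentoalveolar and 3 soft-tissue variables, plus the questionnaire score. Each has a paired t-test row ("Changes in the skeletal effects at pre- and post-intervention", and the equivalent for the other domains) and an ANOVA row for the three groups. No post-hoc procedure is given.

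Section 1.2.2 bases the sample size on the Wits value because "it is one of the parameters that was included in this study and is significant in assessing the skeletal pattern". It does not call Wits primary. The calculation was done "with the consideration of α equals to 0.05, with the power set to 80%, and an effect size of 1.83mm is used".

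Table 3.1 (section 1.3) requires "Cervical Vertebrae Maturity: CS3-CS4 (Growing participants"). By section 1.4, all three arms receive an active appliance: MAA with VBO, MAA without VBO, or Twin Block.

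**The concern.** There are two distinct problems.

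**Between-arm tests.** Seventeen outcomes of equal standing are each tested at 0.05. With 21 participants and no outcome singled out in advance, whichever ANOVA crosses 0.05 can become the finding. The 5% error rate then applies to each test and not to the trial's conclusion about the appliances.

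**Within-group tests.** Participants are selected because they are growing, and no arm is untreated. A skeletal change from T0 to T1 combines the appliance's effect with growth over the same period, and a small p-value does not separate the two. Crediting the whole change to the appliance would overstate its effect to the extent that growth moves the measurement the same way.

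**Working it through.** **The plan's own figure.** The plan states no test count and no familywise error; its only related figure is 5 per group. The SD is not in the readable text, so I take 1.83 as a standardised difference (assumption). With the two-sided normal approximation, n = 2 × (1.960 + 0.842)² / 1.83² = 4.69, so 5 per group. Then 5 × 1.3 = 6.5, rounded to 7, and 3 × 7 = 21. Both match.

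**Counting Table 3.11.**
- Outcomes: 8 + 5 + 3 + 1 = 17.
- ANOVAs: 17.
- Paired tests: 17 × 3 = 51 if run in each arm. Section 1.10.1 describes within-group comparisons for the 16 cephalometric outcomes but does not say so for the questionnaire. If that test is pooled over arms, the count is 16 × 3 + 1 = 49.
- Pairwise follow-up after each ANOVA would add up to 17 × 3 = 51 tests; none is specified.
- Lower anterior facial height is defined in Table 3.7 but absent from Table 3.11, so it is not counted. The reliability ICCs are not counted either.

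**Error across the 17 ANOVAs if no arms differ.**
- Expected false positives: 17 × 0.05 = 0.85, whatever the correlation.
- Chance of at least one, independent outcomes: 1 − 0.95^17 = 0.582.
- By the definitions in Table 3.7, three outcomes follow from others. ANB is SNA minus SNB. The maxillary-mandibular angle follows from the two SN-plane angles. The inter-incisal angle follows from the two incisor angles and the maxillary-mandibular angle.
- The documents give no correlations, so these are assumed. Simulation with 7 per arm and 20,000 runs:

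| Assumed common correlation | 17 outcomes, equal correlation | 14 outcomes plus 3 derived |
|---|---|---|
| 0 | 58% | about 55% |
| 0.3 | 51% | 50% |
| 0.5 | 41% | 43% |
| 0.7 | 30% | 34% |

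At an extreme correlation of 0.9, the equal-correlation figure is still 17%. Allowing for the one Twin Block dropout reported in section 1.6.3.1 (7, 7 and 6 per arm) changes these figures very little.

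**What adjusting all 17 would cost.** Bonferroni gives 0.05 / 17 = 0.0029. At 7 per arm, a two-sided two-arm t-test at 1.83 SD falls from 88% to 43% power. An ANOVA with f = 1.83 / 2 = 0.915 falls from 94% to 61%. The ANOVA figures are optimistic: three arms whose largest gap is 1.83 SD have f of at most 1.83 × √2 / 3 = 0.863. A single primary outcome avoids this loss.

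**The paired tests.** No false-positive count applies here. Overjet shows why: entry requires 7 to 11 mm (Table 3.1), and treatment aims at an edge-to-edge incisal and/or Class I molar relationship (section 1.6.2). A null of no change is implausible by design. The question is what the change can be attributed to, and the design has no untreated comparison to answer it.

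**The case against.** **The outcomes are related, so 58% is too high.** Correct. It is a ceiling, and the three geometric identities rule out full independence. The correction is small, however, and every correlation tried leaves the error well above 5%.

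**A primary outcome may be stated elsewhere.** The trial is said to be registered (section 1.1), and Objectives 1 to 4 are cited in Table 3.11 but not set out in the readable text. The point is therefore limited to what can be read.

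**Between-arm comparison does not remove growth either.** This stands in part. T1 is taken when each participant meets the completion criteria (section 1.7), and follow-up intervals are adjusted as needed (section 1.6.3). Observation time, and with it growth, can differ by arm. Randomisation balances growth potential at baseline in expectation, but not the length of follow-up. With no untreated arm, the ANOVAs compare appliances with each other and cannot show any appliance's own effect.

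**Stronger readings that the documents do not support.** A reader might multiply all the tests by 0.05 and expect that many chance findings. That needs every within-group null to be true, which growth and treatment make implausible. A reader might also infer that the plan will treat significance in one arm but not in another as a difference between arms. Nothing in the text says so; section 1.10.1 assigns between-group questions to ANOVA.

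**Conclusion.** The concern holds as two separate points.

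1. In the readable text, 17 unranked ANOVAs at 0.05 with no primary outcome and no adjustment leave the familywise error on the randomised comparison uncontrolled. If the arms do not differ, 0.85 false positives are expected. The chance of at least one is at most 58%, and about 30% to 51% at assumed common correlations of 0.7 to 0.3. The expected count does not depend on correlation; the probabilities do.

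2. The 51 (or 49) paired tests measure treatment plus growth and cannot credit change to an appliance. This rests on the entry criteria and on the absence of an untreated arm, and needs no arithmetic.

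Both can be put right in analysis and reporting, without new data.

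**What to change.** - **Primary analysis.** Name the between-arm comparison of T0–T1 Wits change, the variable used for the sample size, as the single primary analysis at 0.05. Examine pairwise arm contrasts only after a significant overall ANOVA, and report them with 95% CIs. With three arms, Fisher's protected procedure controls the familywise error: if all arms are equal, the overall test guards at 5%; if only two are equal, just one true null contrast remains.
- **Secondary outcomes.** Report the other 16 as between-arm differences with 95% CIs and no confirmatory significance claims, or apply Holm's adjustment.
- **Within-group change.** Report means with 95% CIs, labelled as treatment plus growth.
- **Conclusions.** Base statements about differences between appliances on between-arm estimates only. Note that T1 timing varies by participant, so growth is not fully removed.
- **Timing.** State the date on which the primary was designated and whether results had been seen. The text is in the past tense and already reports compliance and one dropout, so the designation may be late.

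The cost is a change of wording and reporting. Fewer results can be called significant, and a late designation must be disclosed.

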1.6 Treatment phase

1.6.1 Questionnaire

A questionnaire was given to the participant to be answered prior to the issuance of the appliance. The CPQ questionnaire was selected as it is one of the most widely used instruments globally, with age being a critical factor in assessing patient-reported outcomes in children (Wallander & Koot, 2016). This period, when malocclusion becomes evident following incisor eruption, provided meaningful insights into children requiring interceptive treatment.

The short-form version of CPQ 11-14 consisted of 16 items for patients aged 11–14 years, using closed-ended questions across four domains: oral symptoms, functional limitations, emotional well-being, and social well-being. The instrument captured children's

perceptions and emotional responses regarding their oral health over the preceding four weeks. The CPQ 11–14 had been validated and translated into Bahasa Melayu, and it can be employed in cross-national comparisons because of its similarity to the English-language form. (Amirul et al., 2011)

The CPQ was administered at two time points: prior to appliance issuance (T0) and after the post-advancement phase (T1). Participants completed the questionnaire independently, choosing either the English or Malay version. The principal investigator ([name]) was available if any help was needed by the participants. The CPQ questionnaires are presented in Appendix D.

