Appendix D Child Perceptions Questionnaire (English Version)

Child Perceptions Questionnaire 11-14 (CPQ11-14)

Subject Number:

Age:

Gender:

Date today:

Hello,

Thank you for helping us with our study!

We are doing this study to understand what may happen to children because of their teeth and mouth.

Please Remember:

- Don't write your name on the questionnaire
 - This is not a test, and there are no right or wrong answers
 - Answer as honestly as you can
 - No one you know will see your answers
 - Read each question carefully and think about what has happened to you in the last 4 weeks.
 - Before you answer,ask yourself:"Hasthishappenedtomebecauseofmyteethormouth?"
- Circle the best answer.

A. QUESTIONS ABOUT YOUR TEETH & MOUTH

No	Questions	Never 0	Once/ twice 1	Sometimes 2	Often 3	Every day / Almost every day 4
In the past 4 weeks, have you ever had						
1	Pain in your teeth, lips, jaws, and mouth?	0	1	2	3	4
2	Bad breath / smelly mouth?	0	1	2	3	4
3	Sore spots (ulcers) in your mouth?	0	1	2	3	4
4	Food stuck in between your teeth?	0	1	2	3	4
In the past 4 weeks, have you ever had						
5	Difficult to drink or eat hot or cold foods?	0	1	2	3	4
6	Difficulty biting or chewing food like apples, corn on the cob or steak?	0	1	2	3	4
7	Difficulty saying any words?	0	1	2	3	4
8	Taken longer than others to eat a meal?	0	1	2	3	4

B. QUESTIONS ABOUT YOUR FEELING.**In the past 4 weeks, have you ever felt**

9	Been upset because of your teeth or mouth?	0	1	2	3	4
10	Irritable or frustrated because of your teeth or mouth?	0	1	2	3	4
11	Shy or embarrassed because of your teeth or mouth?	0	1	2	3	4
12	Been concerned what other people think about your teeth, lips, mouth or jaws?	0	1	2	3	4

C. QUESTIONS ABOUT YOU BEING WITH OTHER PEOPLE**In the past 4 weeks, have you ever**

13	Had other children ask you questions about your teeth, lips, jaws or mouth?	0	1	2	3	4
14	Other children teased you or called you names?	0	1	2	3	4
15	Avoided smiling or laughing when around other children?	0	1	2	3	4
16	Argued with other children or your family because of your teeth or mouth?	0	1	2	3	4

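### The CPQ scoring rule in section 1.10.1 (1 to 5) contradicts the English form in Appendix D (0 to 4); the handling of out-of-range ages and the timing of the T0 questionnaire also need stating

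*Combined protocol and SAP*

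**What the plan says.** **Scoring.** Section 1.10.1 (Statistical Tests) records responses as "never' = 1, 'hardly ever' = 2, 'sometimes' = 3, 'fairly often' = 4, and 'very often' = 5". Totals are then compared by paired t-test (before against after) and one-way ANOVA (between groups). The English form in Appendix D has five printed columns starting at 0, the last being "Every day / Almost every day 4". No rule converts one coding to the other.

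**Instrument and ages.** Section 1.6.1 says that the short form "consisted of 16 items for patients aged 11–14 years". Table 3.1 in section 1.3 admits participants aged "10-14 years old (Female), 12-16 years old (Male". No age restriction, alternative version or sensitivity analysis is given for the CPQ.

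**Timing.** Section 1.6.1, which stands under the treatment phase, gives the two administrations as "prior to appliance issuance (T0) and after the post-advancement phase (T1".

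**The concern.** The CPQ total is the only outcome for Objective 4. The scoring rule and the English form disagree in numbers and in labels, so the documents do not define the scale on which that total is reported. A circled 1 means once or twice on the form, but 1 means never in section 1.10.1. Section 1.6.1 gives suitability for cross-national comparison as a merit of the instrument, and an undeclared offset of 16 points would defeat that. The label mismatch also leaves a reader unsure which response wording the children saw.

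Two further matters affect how the scores can be read. Some eligible participants are outside the age range stated for the instrument. And the T0 score may have been given by children who already knew their arm, since section 1.4 limits blinding to data analysis.

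**Working it through.** The documents state no CPQ total, range, effect size or power (section 1.2.2 bases the sample size on the Wits value), so there is no figure of the plan's own to reproduce.

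**1. The two codings side by side**

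| Category | Appendix D | Section 1.10.1 |
|---|---|---|
| Lowest | Never, 0 | never, 1 |
| Second | Once/twice, 1 | hardly ever, 2 |
| Third | Sometimes, 2 | sometimes, 3 |
| Fourth | Often, 3 | fairly often, 4 |
| Highest | Every day or almost every day, 4 | very often, 5 |

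All five numbers differ, and so do three of the five labels.

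**2. Range of the total.** Inputs: 16 items (section 1.6.1) and the lowest and highest codes above.
- Form: 16 × 0 = 0 to 16 × 4 = 64.
- Section 1.10.1: 16 × 1 = 16 to 16 × 5 = 80.
- Difference for every complete questionnaire: 16 × 1 = 16.

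**3. Effect on the planned tests.** Let X0 and X1 be the T0 and T1 totals on the form's scale.
- 1 to 5 at both times: (X1 + 16) − (X0 + 16) = X1 − X0. The change, the paired t and the ANOVA F stay the same.
- Percentage change: 100 × (X1 − X0)/X0 becomes 100 × (X1 − X0)/(X0 + 16), which is nearer to zero.
- 0 to 4 at T0 and 1 to 5 at T1: (X1 + 16) − X0 = (X1 − X0) + 16, a false change of 16 points. If this happened for one participant in an arm of 7, the arm's mean change would move by 16/7 ≈ 2.3 points.

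**4. Numerical check.** These are simulated responses, not trial data: 21 participants, 7 per arm, 16 items.

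| Quantity | 0 to 4 | 1 to 5 |
|---|---|---|
| Mean at T0 | 33.5 | 49.5 |
| Mean at T1 | 28.7 | 44.7 |
| Mean change | −4.86 | −4.86 |
| Percentage change | −14.5% | −9.8% |
| Paired t | −5.70 | −5.70 |
| ANOVA F on change (p) | 1.73 (0.205) | 1.73 (0.205) |
| ANOVA F on T1 totals (p) | 1.95 (0.172) | 1.95 (0.172) |

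Mixing the codings between T0 and T1 added exactly 16 points.

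**5. Ages.** Girls are eligible over five years of age (10 to 14), of which one lies outside 11 to 14: 1/5 = 20%. Boys are eligible over five (12 to 16), of which two lie outside: 2/5 = 40%. If ages were uniform, the share would lie between 20% (all girls) and 40% (all boys), and would be 30% with equal sexes. This is illustration only. Eligibility also requires cervical stage CS3 to CS4, which makes uniform ages doubtful, and actual ages are not given.

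**6. Timing.** Points towards completion after allocation:
- The questionnaire is described under the treatment phase and is not in the section 1.5 list of pre-treatment procedures.
- Section 1.5.5 has alginate impressions taken for the control group, within the pre-treatment phase.
- Section 1.5.6 says that the pre-treatment flow chart runs through selection and preparation of the intervention.
- Section 1.6.2 puts delivery about three weeks after that phase.

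Points that leave it open:
- The text fixes the questionnaire only as before the appliance was issued and labels it T0, the label of the pre-treatment phase.
- The intra-oral scan was taken on all participants, so it reveals no arm.
- No section says when participants learned their arm.

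**The case against.** The strongest reply is that the scoring conflict has no inferential effect: a constant shift changes no mean difference, t, F or p-value. That stands, provided one coding was used throughout.

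A reader might infer that the trial's totals are 16 points too high. The documents do not support this. They report no CPQ scores, and if the circled digits were entered as printed, the data already lie on 0 to 64 and section 1.10.1 is only a write-up error. Nor is Appendix D the only form: participants could choose Malay, and that version is not available for checking. The contradiction is therefore established for the English form alone.

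A reader might also infer that blank items were summed as nothing and so fell below never. No section says how blanks were handled. Under 0 to 4 such a blank would count as never, so the choice of coding does not settle that question.

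On age, it is tempting to make participants aged 11 to 14 at both administrations the main analysis. That conflicts with section 1.8, which keeps all enrolled participants in the analysis. T1 falls when advancement is complete, so age at T1 depends partly on the duration of treatment, and the restriction would select on a post-randomisation variable.

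On timing, a reader might conclude that the T0 score was taken after allocation and already reflects a reaction to the assigned appliance. The first part is a reasonable inference but is not stated; the second is conjecture. On any reading the score precedes appliance wear.

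**Conclusion.** The scoring contradiction is plain on the face of the documents for the English form, and it should be corrected. Its size is a constant 16 points on each complete total (16 to 80 against 0 to 64). It affects the Objective 4 means, percentage changes and any comparison with scores on the form's scale. It does not affect the planned tests unless codings were mixed, in which case the error is up to 16 points per participant.

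The age mismatch is equally plain, but its extent is unknown. The 20% to 40% range rests on uniform ages, which the documents do not give.

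The timing matter is a gap in the description and not a demonstrated fault. The cephalometric objectives are untouched by all three.

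**What to change.** 1. **Scoring.** In section 1.10.1, score items 0 to 4 with the labels printed on the form and state the total range of 0 to 64, after confirming that the Malay form uses the same scale. Check the entered data against the completed forms at both time points. Cost: one wording change and a check of about 21 participants' forms (two each).
2. **Age.** Keep the all-participant intention-to-treat analysis as the main one. Report how many participants were outside 11 to 14, which the dates of birth collected under Table 3.3 will show. Add a sensitivity analysis limited to those aged 11 to 14 at T0, which is fixed before any appliance wear. Downside: low precision, since the arms have only about 7 participants before any restriction.
3. **Timing.** Report when the T0 questionnaire was completed relative to allocation and to its disclosure. If it came after allocation, call it a post-allocation, pre-wear baseline. The documents describe the trial as already conducted, so moving the form to an earlier visit is not an option. Cost: a sentence or two of reporting.
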